4.2.5. Elimination from Per-protocol analysis Set for Immunogenicity (PPS-I)

4.2.5.1. Excluded participants from Per-protocol analysis set for immunogenicity of maternal participants

A participant will be excluded from the PPS immunogenicity analysis under the following conditions:

Table 7 Elimination code and condition for maternal participants

Code	Condition under which the code is used	Visit (timepoints) where the code is applicable
800	Fraudulent data	All
900	Invalid informed consent	All
1030	Study vaccine not administered	All
1040.Vx+*	Administration of concomitant vaccine(s) forbidden in the protocol	All
1050	Randomisation failure	All
1060	Randomisation code was broken	All
1070*	Mother got vaccinated with the correct vaccine but incorrect volume	All
1070*	Vaccination not according to protocol (site of injection, route of administration, wrong replacement of study treatment administered)	All
1070*	Study treatment not prepared as per protocol (e.g. reconstitution)	All
1070*	Other deviations related to wrong study treatment/administration/dose	All

Code	Condition under which the code is used	Visit (timepoints) where the code is applicable
1070*	Study treatment administered while contraindicated	All
1080	Vaccine temperature deviation	All
1090	Expired vaccine administered	All
2010	Protocol violation (inclusion/exclusion criteria)	All
2040.Vx+*	Administration of any medication/product forbidden by the protocol	Visit 2/Day 31, Visit 3/Delivery
2050.Vx+*	Intercurrent medical conditions which are exclusionary as per protocol	Visit 2/Day 31, Visit 3/Delivery
2060.Vx+*	Concomitant infection related to the vaccine which may influence immune response	Visit 2/Day 31, Visit 3/Delivery
2070.Vx+*	Concomitant infection not related to the vaccine but may influence immune response	Visit 2/Day 31, Visit 3/Delivery
2090.Vx	Participants did not comply with blood sample schedule: 
 For PPS at Visit 2/Day 31, check the interval from vaccination to day 31 BS = -10/+15 days; For PPS at Visit 3/Delivery, check the interval from delivery to delivery BS = -1/+3 days 	Visit 2/Day 31, Visit 3/Delivery
2100.Vx	Serological results not available (immunogenicity sample collected but invalid/no result)	Visit 1/Day 1 Visit 2/Day 31, Visit 3/Delivery
2120.Vx	Obvious incoherence or abnormality or error in the data	Visit 2/Day 31, Visit 3/Delivery
2130.Vx	Testing performed on serology samples not aligned with ICF	Visit 2/Day 31, Visit 3/Delivery
2110.Vx	Immunogenicity sample collected but GSK decided not to test	Visit 1/Day 1 Visit 2/Day 31, Visit 3/Delivery

* Attribution of these elimination codes to participant need CRDL review of individual listing
.Vx+ indicates participants whose immunogenicity data will be eliminated from a specific visit onwards;
.Vx indicates participants whose immunogenicity data will be eliminated from a specific visit.

4.2.5.2. Excluded participants from Per-protocol immunogenicity (PPS-I) analysis set of infant participants

An infant participant will be excluded from the PPS immunogenicity analysis under following conditions:

Table 8 Elimination code and condition for infant participants

Code	Condition under which the code is used	Visit (timepoints) where the code is applicable
800, 800#	Fraudulent data	All
900, 900#	Invalid informed consent	All
1030#	Study vaccine not administered	All
1040.Vx##+*	Administration of concomitant vaccine(s) forbidden in the protocol	All
1050#	Randomisation failure	All
1060#	Randomisation code was broken	All
1070#*	Mother got vaccinated with the correct vaccine but incorrect volume	All
1070#*	Vaccination not according to protocol (site of injection, route of administration, wrong replacement of study treatment administered)	All
1070#*	Study treatment not prepared as per protocol (e.g. reconstitution)	All
1070#*	Other deviations related to wrong study treatment/administration/dose	All
1070#*	Study treatment administered while contraindicated	All
1080#	Vaccine temperature deviation	All
1090#	Expired vaccine administered	All
2010, 2010#	Protocol violation (inclusion/exclusion criteria)	All
2040#*	Administration of any medication/product forbidden by the protocol	All
2140.#*	Administration of any medication/product forbidden by the protocol	All
2040Vx*	Administration of any medication/product forbidden by the protocol	Visit 1-NB/Birth Visit 2-NB/Day 43 post-birth ^a Visit 3-NB/Day 121 post-birth ^a Visit 4-NB/Day 181 post-birth ^a
2140Vx*	Administration of any medication/product forbidden by the protocol (leading to elimination from PPS-I)	Visit 1-NB/Birth Visit 2-NB/Day 43 post-birth ^a Visit 3-NB/Day 121 post-birth ^a Visit 4-NB/Day 181 post-birth ^a

CONFIDENTIAL

212171 (RSV MAT-009)
Statistical Analysis Plan Amendment 5

Code	Condition under which the code is used	Visit (timepoints) where the code is applicable
2050.Vx#*	Intercurrent medical conditions which are exclusionary as per protocol	All
2050.Vx*	Intercurrent medical conditions which are exclusionary as per protocol	All
2060.Vx#+* 2060.Vx+*	Concomitant infection related to the vaccine which may influence immune response	All
2070.Vx#+* 2070.Vx+*	Concomitant infection not related to the vaccine but may influence immune response	All
2090.Vx	Participants did not comply with blood sample schedule 
 • For PPS at Visit 1/Day 1 check the interval of day 1 BS -0/+3 days; • For PPS at Visit 2/Day 43 post-birth, check the interval of day 43 BS -12/+18 days; • For PPS at Visit 3/Day 121 post-birth, check the interval of day 121 BS -10/+20 days; • For PPS at Visit 4/Day 181 post-birth, check the interval of day 181 -15/+20 days 	Visit 1-NB/Birth Visit 2-NB/Day 43 post-birth ^a Visit 3-NB/Day 121 post-birth ^a Visit 4-NB/Day 181 post-birth ^a
2100.Vx	Serological results not available (immunogenicity sample collected but invalid/no result)	Visit 1-NB/Birth Visit 2-NB/Day 43 post-birth ^a Visit 3-NB/Day 121 post-birth ^a Visit 4-NB/Day 181 post-birth ^a
2120.Vx	Obvious incoherence or abnormality or error in the data	Visit 1-NB/Birth Visit 2-NB/Day 43 post-birth ^a Visit 3-NB/Day 121 post-birth ^a Visit 4-NB/Day 181 post-birth ^a
2130.Vx	Testing performed on serology samples not aligned with ICF	Visit 1-NB/Birth Visit 2-NB/Day 43 post-birth ^a Visit 3-NB/Day 121 post-birth ^a Visit 4-NB/Day 181 post-birth ^a
2110.Vx	Immunogenicity sample collected but GSK decided not to test	Visit 1-NB/Birth Visit 2-NB/Day 43 post-birth ^a Visit 3-NB/Day 121 post-birth ^a Visit 4-NB/Day 181 post-birth ^a
3100	Birth is less than 4 weeks post-vaccination.	All

* Attribution of these elimination codes to participant need CRDL review of individual listing

Carry forward elimination from mother to infant

Vx+ indicates participants whose immunogenicity data will be eliminated from a specific visit onwards;

Vx indicates participants whose immunogenicity data will be eliminated from a specific visit.

^a As per Protocol Amendment 4, infant blood samples will not be collected at V2-NB, V3-NB and V4-NB. 2090.Vx, 2100.Vx, 2120.Vx, 2130.Vx will not be applicable to infant participants whose blood samples are not collected under Protocol Amendment 4.

4.2.6. Elimination from solicited safety set

4.2.6.1. Excluded participants from Solicited safety set

Code 1030 (Study vaccine not administered at all), code 800 (fraudulent data), code 900 (invalid informed consent) and code 1160 (no post-vaccination solicited safety data only for Stage A participants) will be used for identifying participants eliminated from the solicited safety set.

5. STATISTICAL ANALYSES

Standard data derivation rules and stat methods are described in section 10.1 while the study specific data derivation rules and stat methods are described in section 9.

5.1. Demography

5.1.1. Analysis of demographics/baseline characteristics planned in the protocol

These analyses will be performed on the Exposed set (ES) for maternal and infant participants and on the modified Full Analysis - Efficacy set (modified FAS-E) for infant participants. Analysis may also be repeated on the Per Protocol set for immunogenicity for maternal as well as infant participants.

For all maternal participants, demographic characteristics (e.g., age at vaccination (18-34, 35-39, ≥ 40 years of age), gestational age at vaccination ($24^{0/7}$ - $28^{0/7}$, $28^{1/7}$ - $34^{0/7}$ weeks), geographic ancestry) will be summarized by group and overall using descriptive statistics. The interval in days between maternal vaccination and delivery will be calculated and summarized by group using descriptive statistics.

For their infants, demographic characteristics (e.g., gestational age at time of delivery (≥ 37 weeks; < 37 weeks), sex, weight, length, head circumference, geographic ancestry, apgar score), and lifestyle characteristics (e.g., living environment, household composition, breastfeeding, passive smoking and extent of contact with children less than 6 years of age) will be summarised by group, and for each immunogenicity sub-cohort within each group, using descriptive statistics.

- Frequency tables will be generated for categorical variables such as gestational age at time of delivery (≥ 37 weeks; < 37 weeks).
- Mean, median, standard deviation and range will be provided for continuous data such as age.

Demographics and baseline characteristics as well as the lifestyle characteristics may be reported by geographic region and by economic region (LMIC and HIC).

5.1.2. Additional considerations

Demographic characteristics will also be summarized on the Enrolled Set for public disclosure.

Subgroup analysis for demographic characteristics by age category at vaccination (18 – 34, 35-39; ≥ 40 years) for maternal participants and by gestational age at birth (≥ 37 weeks or < 37 weeks) for infant participants will also be performed on ES or modified FAS-E for infant participants.

Participants disposition will be summarized by group using descriptive statistics:

- Number of maternal participants enrolled, randomised, vaccinated, eligible for maternal efficacy populations and withdrawn including withdrawal reasons in each group and overall will be tabulated.
- Number of infants enrolled, eligible for infant efficacy populations and withdrawn including withdrawal reasons will be tabulated by group, by sub-cohort within each group and overall.

Vital signs will not be summarized for this study.

[figure not shown]
[figure not shown]
[figure not shown]
Summary of important protocol deviations leading to elimination will be tabulated by group and overall. An individual listing will also be provided.

Summary of medical history will be performed on ES by Medical Dictionary for Regulatory Activities (MedDRA) and preferred term.

5.2. Efficacy

5.2.1. Analysis of primary efficacy endpoints planned in the protocol

The primary analysis of vaccine efficacy (VE) will be based on the modified Full Analysis - Efficacy set for infants (modified FAS-E). A secondary analysis based on the Full Analysis – Efficacy set (FAS-E) and the Per Protocol - Efficacy set for infants will be performed to complement the modified FAS-E analysis.

Primary Efficacy Endpoints – Infant participants	Statistical Analysis Methods

From birth to 6 months, occurrences of medically assessed, RSV-associated severe LRTIs according to the case definitions.
 
OR
 
From birth to 6 months, occurrences of any medically assessed, RSV-associated LRTIs according to the case definitions.
	
CCI
 

CCI
 	

CCI

5.2.1.1. Sensitivity Analyses

Supportive analysis of time to confirmed RSV-LRTI of any severity and time to confirmed severe RSV-LRTI will be conducted by using Kaplan-Meier cumulative incidence curves.

Sub-group analyses by regions and by key demographic characteristics may also be explored. In addition, efficacy analyses stratified by VE reported for geographic regions (North America, Central America & Caribbean, and South America), economic regions (LMIC and HIC), RSV type and RSV seasonality (year-round circulation and seasonal circulation) may be included in the clinical study report.

Supportive analyses on primary efficacy endpoints based on the modified FAS-E will also be conducted for RSV-associated LRTI cases confirmed by central laboratory tests and PCR confirmed local laboratory tests and by all RSV tests (central and all local laboratory tests).

[figure not shown]

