### Overall rationale for the current amendment:

This protocol has been amended to reflect the following:

- The Benefit/Risk assessment has been updated to clarify that:
  - The observed numerical imbalance in neonatal deaths is not an independent safety signal but a consequence of the validated signal of preterm births.
  - Based on the evaluation of the Study Day 43 post-birth interim analysis, GSK concluded that preterm birth is an identified risk for the pregnant women population, for the RSV Maternal vaccine candidate.
  - GSK has discontinued the work on this RSV Maternal vaccine candidate and is closing out all ongoing vaccine trials. GSK will continue to monitor and follow-up the immunized participants in the trials for the duration specified in the respective protocols.
- For vaccine efficacy (VE) related objectives, the sensitivity and supportive analyses will be only conducted for primary efficacy endpoints, but the sensitivity analysis using the negative binomial model has been removed.
- The following changes have been made to the secondary efficacy endpoints:
  - For efficacy endpoint from birth to 7 months and above, only the efficacy endpoints of “From birth (Visit 1-NB) to 12 months (Visit 5-NB), occurrences of severe medically assessed, RSV-associated LRTIs” and “From birth (Visit 1-NB) to 12 months (Visit 5-NB), occurrences of any medically assessed, RSV-associated LRTIs” will be kept, and the analyses will be conducted by using Kaplan-Meier curves from birth to 12 month, so that the VE changes across time can be observed.
  - “From birth (Visit 1-NB) to 6 months (Visit 4-NB), occurrences of any medically assessed, RSV-associated LRTIs by alternative case definitions” has been removed.
  - “From birth (Visit 1-NB) to 12 months (Visit 5-NB), time to the first occurrence of severe medically assessed, RSV-associated LRTIs according to the case definition” has been removed.
  - “From birth (Visit 1-NB) to 12 months (Visit 5-NB), time to the first occurrence of any medically assessed, RSV-associated LRTIs according to the case definition” has been removed.

- Secondary efficacy endpoints on infant participants will only be assessed in the Modified Full Efficacy set (FAS) and Secondary efficacy endpoints on maternal participants will only be assessed in the Exposed Set (ES).

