#### **6.3.6. Blinding and unblinding**

To minimize the introduction of bias, this study will be double-blinded\*. Participants will not have access to their randomization assignment, and investigators and their staff will be blinded to the participant's assigned study intervention throughout the course of the study.

The laboratory in charge of the sample testing will be blinded to the intervention assignment. Codes will be used to link the participant and study (without any link to the intervention attributed to the participant) to each sample.

A firewall will be established to ensure that data are not inadvertently unblinded. Details are provided in a separate Firewall charter.

*\* Following the decision to stop enrollment and vaccination, the study/site staff and maternal participants no longer stay blinded. Refer to Section 2.3 for details.*

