**8.4.1.2. Respiratory tract illnesses (RTIs) in infant participants**

RTI symptoms include:

- Nasal discharge running freely out of the infant's nose (runny nose),
- Breathing through the mouth because the infant's nose is blocked (blocked nose),
- Regular bursts of cough,
- Difficulty in breathing (fast breathing, poor feeding, working hard to breathe, or making unusual sounds when breathing), and
- Wheezing (a whistling sound when the infant breathes out, and thus another sign of potential difficulty in breathing).

**Worsening** means any clinically observed/diagnosed symptoms and signs that are reported during the same respiratory tract illness and reflect a deterioration in the infant's respiratory tract functions.

A *potential* lower respiratory tract **illness** (LRTI) is one in which the infant's RTI symptoms include at least one of the following:

- Difficulty in breathing (fast breathing, poor feeding, working hard to breathe, or making unusual sounds when breathing);
- Wheezing (a whistling sound when the infant breathes out);
- Parental concern (the parent(s)/LAR(s) or their designate(s) are concerned about the infant's respiratory tract illness, or general health in the context of the respiratory tract illness and intend to seek medical care).

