5.2.2. Analysis of secondary efficacy endpoints planned in the protocol

The primary analysis of VE on secondary efficacy endpoints **in infants** will be based on the modified Full Analysis - Efficacy set (modified FAS-E). **The analysis of vaccine efficacy in maternal participants will be based on the Exposed set.**

Secondary Efficacy Endpoints	Statistical Analysis Methods

From birth (Visit 1-NB) to 6 months (Visit 4-NB), occurrences of RSV-associated hospitalizations according to the case definitions.
 
From birth (Visit 1-NB) to 6 months (Visit 4-NB), occurrences of all-cause LRTIs
	
CCI
 

From birth (Visit 1-NB) to 6 months (Visit 4-NB), occurrences of all-cause LRTIs with hospitalization
	

From birth (Visit 1-NB) to 12 months, occurrences of severe medically assessed, RSV-associated LRTIs according to the case definitions
	

From birth (Visit 1-NB) to 12 months, occurrences of any medically assessed, RSV-associated LRTIs according to the case definitions.
	

From birth (Visit 1-NB) to 6 months (Visit 4-NB), occurrences of severe medically assessed, RSV-associated LRTIs according to the case definition, for RSV subtype A and RSV subtype B separately.
	

From birth (Visit 1-NB) to 6 months (Visit 4-NB), occurrences of any medically assessed, RSV-associated LRTIs according to the case definition, for RSV subtype A and RSV subtype B separately.
	

Secondary Efficacy Endpoints	Statistical Analysis Methods
From birth (Visit 1-NB) to 4 months (Visit 3-NB), occurrences of severe medically assessed, RSV-associated LRTIs according to the case definition.	CCI
From birth (Visit 1-NB) to 4 months (Visit 3-NB), occurrences of any medically assessed, RSV-associated LRTIs according to the case definitions	
From birth (Visit 1-NB) to 6 months (Visit 4-NB), occurrences of all-cause pneumonia	
From study intervention administration (Visit 1) to 6 months post-delivery (Contact 1), occurrence of RSV-associated medically attended RTIs (RSV-MA-RTIs)	
From birth (Visit 1-NB) to 12 months (Visit 5-NB), occurrences of RSV-associated hospitalizations according to the case definitions.	

CCI

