8. CHANGES FROM PLANNED ANALYSES

- By-participant listings of SAEs, AEs leading to study withdrawal, MAEs, adverse pregnancy outcomes and pregnancy related AESIs will be prepared and released. Such listings have already been released in earlier analyses. Due to study enrolment/vaccination stop, the study has been unblinded already before the final analysis.
- A sensitivity analysis for immunogenicity results excluding participants from Bangladesh, for which HIV testing was not performed before their enrollment into the study, has been added.
- Between group evaluations for immunogenicity analysis was clarified to be performed among RSV MAT and Control instead of vaccination groups, the wording has been corrected.
- In February 2022, enrollment and vaccination were stopped because of an imbalance in preterm births and associated neonatal deaths observed between the RSVPreF3-Mat and placebo groups. Subsequently the study was unblinded, and therefore the presented VE endpoints are descriptive.
- Subgroup analyses by economic region (LMIC and HIC) will be performed for demography, efficacy, and safety evaluations.
- Subgroup analyses by gestational age at birth will be performed for demography and safety evaluations.
- Sensitivity analysis for primary efficacy endpoints by using a negative binominal regression model have been removed.

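### Later infant follow-up is more often open-label, and the readable plan does not separate this from a true change in vaccine efficacy with age

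*SAP*

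**What the plan says.** **Reading VE over age.** The rationale for Protocol Amendment 5 keeps the two birth-to-12-month LRTI endpoints and says that "the analyses will be conducted by using Kaplan-Meier curves from birth to 12 month, so that the VE changes across time can be observed". SAP 5.2.1.1 lists the curves as supportive: "Supportive analysis of time to confirmed RSV-LRTI of any severity and time to confirmed severe RSV-LRTI will be conducted by using Kaplan-Meier cumulative incidence curves". The VE windows all start at birth. SAP 5.2.1 covers 0-6 months, and SAP 5.2.2 adds shorter and longer windows, for example "From birth (Visit 1-NB) to 4 months (Visit 3-NB), occurrences of any medically assessed" and "From birth (Visit 1-NB) to 12 months, occurrences of any medically assessed, RSV-associated LRTIs according to the case definitions".

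**Loss of blinding.** Protocol 6.3.6 notes: "Following the decision to stop enrollment and vaccination, the study/site staff and maternal participants no longer stay blinded". Protocol 10.6.4 dates the enrolment stop to 25 February 2022. The unblinding notes came in with Amendment 4, dated 15 March 2022 (Protocol 10.11). No unblinding date is given. Infant surveillance runs to 12 months (Protocol 8.4.2.2).

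**Case-finding.** An infant assessment visit is triggered by reported difficulty in breathing, by wheeze, or by parental concern about the illness "or general health in the context of the respiratory tract illness and intend to seek medical care" (Protocol 8.4.1.2 and 8.4.3.2). The endpoint requires evaluation by a healthcare professional (Protocol Table 4, footnote 1).

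**Response to unblinding.** SAP 8 says: "Subsequently the study was unblinded, and therefore the presented VE endpoints are descriptive". A footnote to SAP Table 6 says that the study-wide unblinding does not count as a broken randomisation code, so the per-protocol set does not remove open-label follow-up either.

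**The concern.** A case enters the analysis only if someone reports symptoms and an assessment follows. From some date in 2022, the parents who report and the staff who respond knew the arm. Unblinding fell on a calendar date, so the share of open-label follow-up rises with infant age.

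Suppose mothers in one arm became more or less ready than mothers in the other to report symptoms or seek care. VE would then appear to move with age although true protection had not changed. Knowledge of a safety signal could shift reporting in the vaccine arm, and knowledge of having had placebo could shift it in the control arm. More visits also give more chances to qualify, because the case definition uses the lowest SpO2 monitored (SAP Table 12). Labelling VE descriptive settles the question of formal inference. It does nothing about differential ascertainment in results marked for public disclosure (SAP 7.1).

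**Working it through.** The current plan has no hypothesis test for VE (Protocol 9.1) and states no figure on this point, so there is nothing to reproduce. The check asks how fast the blinded share falls with age and what that could do to VE.

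**Inputs from the documents.** Vaccination at 24 0/7 to 34 0/7 weeks of gestation; year-round enrolment; vaccination stopped on 25 February 2022; infant surveillance from birth to 12 months.

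**Assumptions, not in the documents.** First vaccination on 5 October 2020, 20 November 2020 or 1 March 2021; uniform or rising accrual; gestational age at vaccination uniform over the permitted range; birth near 39 weeks; unblinding on 25 February, 15 March or 15 June 2022; complete follow-up; constant RSV hazard. This gives 18 combinations, each simulated with 400,000 infants. The central case is 20 November 2020, uniform accrual and 15 March 2022.

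**Blinded share of follow-up, b**

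| Age | Central | Range over the 18 |
|---|---|---|
| 0-4 months | 75% | 42-94% |
| 4-6 months | 56% | 15-78% |
| 6-12 months | 29% | 2-54% |
| 0-6 months | 69% | 33-89% |
| 0-12 months | 49% | 17-71% |

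The share falls with age in every combination. The two kinds of follow-up still overlap: in the central case about 12% of infants are born after unblinding, and about 9% complete 12 months blinded.

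**Effect on VE.** Let a be the vaccine-to-placebo ratio of case ascertainment in open-label time, taken as 1 in blinded time. Then

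apparent VE = 1 - (1 - VE) × [b + (1 - b) × a].

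With constant true VE of 60% (assumed) and the central shares:

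| a | 0-4 | 0-6 | 0-12 | 4-6 only | 6-12 only |
|---|---|---|---|---|---|
| 1.0 | 60.0% | 60.0% | 60.0% | 60.0% | 60.0% |
| 1.2 | 58.0% | 57.5% | 55.9% | 56.5% | 54.3% |
| 0.8 | 62.0% | 62.5% | 64.1% | 63.5% | 65.7% |
| 1.5 | 55.0% | 53.8% | 49.8% | 51.2% | 45.8% |

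Worked example for 0-12 months, a = 1.2: 0.49 + 0.51 × 1.2 = 1.102; 1 - 0.4 × 1.102 = 55.9%.

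**Apparent trend with age.** The gap between two windows is (1 - VE) × (a - 1) × (difference in b). For a = 1.2:

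- 0-4 against 0-12 months, central: 0.4 × 0.2 × (0.75 - 0.49) = 2.1 points. Over the 18 combinations the difference in b is 0.23 to 0.42, giving 1.8 to 3.4 points.
- 0-4 against 6-12 months, central: 0.4 × 0.2 × (0.75 - 0.29) = 3.7 points. Over the 18 combinations the difference is 0.40 to 0.70, giving 3.2 to 5.6 points.
- Departure of the 0-12 month estimate from 60%: 0.08 × (1 - b), with b from 0.71 to 0.17, giving 2.3 to 6.6 points.

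**The case against.** **What stands.**

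- Bias needs a between-arm difference. An equal change in both arms leaves VE unbiased (the a = 1.0 row), and nothing in the documents shows that reporting shifted in either direction.
- Safeguards reduce the risk. Active contacts are scripted, on a schedule that does not depend on arm (Protocol 8.4.2.2.1). Visit triggers are fixed. Cases need SpO2 or respiratory-rate criteria plus confirmed RSV (SAP Table 12). The laboratory is to be blinded (Protocol 6.3.6).
- The Protocol Table 4 objectives are cumulative from birth. None is a waning objective, and the purpose of observing VE over time appears in the amendment rationale, not in SAP 5.2.1.1.
- The 6-month analysis has already been done (SAP 7.1), so new primary-endpoint estimates would be post hoc, and development of the candidate has stopped.
- Censoring at a calendar date also changes the mix of RSV seasons.

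**What does not stand.** Scripted contacts still collect parental reports, and a blinded laboratory protects only the swabs that were taken. The descriptive label does not correct an estimate.

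**Stronger readings that the documents do not support.** A reader might infer that waning cannot be separated from unblinding at all. Births were staggered around a calendar date, so blinded and open-label follow-up coexist at the same ages, at least the younger ones. A reader might also infer that the plan has no censoring rule. The detailed VE methods in SAP 5.2.1 and 5.2.2 and Protocol 9.4.3 and 9.4.4 are redacted, so a rule there cannot be excluded.

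**Conclusion.** The concern holds in a limited form. The sponsor intends to look at VE across the first year, follow-up at later ages is more often open-label, and nothing in the readable text separates the two.

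Any bias depends on an unverified difference in ascertainment between arms and could mimic or mask waning. For an assumed 20% shift at 60% VE, the spread between the planned cumulative windows is about 2 points (1.8 to 3.4), and the later part of the curves is more exposed (3.2 to 5.6 points between 0-4 and 6-12 months). These sizes rest on assumed accrual, an assumed unblinding date and a constant RSV hazard; seasonal transmission would change them.

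It would go too far to say that the reported VE is biased, or that the trial can say nothing about durability. The supported statement is that the readable plan gives no means of telling a change in protection from a change in ascertainment, and that after 6 months there may be little blinded time (2-54%) with which to try.

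**What to change.** If the redacted methods already contain a rule for follow-up after unblinding, the sponsor need only point to it. Otherwise, in SAP 5.2.1.1 and 5.2.2:

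1. State the unblinding date, by site or mother if recorded.
2. Add a supportive analysis on modified FAS-E of the two primary VE estimates and the birth-to-12-month Kaplan-Meier curves, with infants censored at unblinding. If individual dates were not recorded, censor conservatively at 25 February 2022. Show it beside the pooled results and label it post hoc for the primary endpoints.
3. Report blinded person-time by age band and arm.
4. Note that calendar censoring also alters the RSV-season mix.
5. Where blinded time after 6 months is too thin, state that an apparent change in VE with age cannot be attributed to waning or persistence.

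The cost is a few extra tables and figures and wider intervals, most of all after 6 months. Infants born after the censoring date contribute nothing to this analysis. The pooled analyses remain as planned.
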